## Purpose of the Study

This project will use Self-system therapy (SST), an empirically validated intervention based to treat depression and lung-cancer-related distress in older adults (65 years and older). We hypothesize that psychological measures and physical performance measures as indicators of resilience will be acceptable and feasible to participants.

(Hypothesis 1) Participants will complete at least 80% of SST treatment sessions (Hypothesis 2). There will be an association between measures of psychological and physical resilience. (Hypothesis 3). Lastly, we hypothesize that participant's psychological and physical resilience scores will improve from baseline to post-intervention as a function of receiving the SST intervention.

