#### Design & Procedures

Fifteen older adults (ages 65 and older) will be recruited from clinics of the Duke Cancer Institute.

Older adults with lung cancer will receive the SST intervention with sessions that range between 8 (recommended minimum number of sessions) to a maximum of 12 sessions lasting on average of 30-45 minutes. The intervention will be delivered by video conference. The design is a single-arm study, with no control or placebo group condition.

The four content/topic areas that are covered across the 8-12 SST intervention sessions are as follows:

1) Orientation Phase of SST. Participants are provided with a rationale for treatment that focuses on the importance of self-regulation for well-being in the context of advanced cancer.

2) Exploration Phase of SST. This phase consists of having patients examine successful and unsuccessful interpersonal interactions, functional difficulties, and their self-evaluations and goal pursuit strategies while coping with advanced cancer. Patients then identify and analyze their explicit or implicit preferences for certain kinds of personal goals.

3) Adaptation Phase of SST. The patient and interventionist work together to address each treatment goal, using change strategies and compensatory strategies that include helping the patient to modify goals or to learn to pursue them via different means that are a better fit to their current life circumstances, physical, limitations, or personality traits.

4) A maintenance plan is developed with each patient. The maintenance plan includes a list of strategies to be used daily (e.g. self-monitoring forms), short-term goals (e.g. becoming more active in self-rewarding activities) and long-term goals.

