#### Subject Recruitment

Potentially eligible candidates will be identified from each oncology provider's clinic schedules via medical chart review. This pre-identification process involves pre-screening of patients using their medical records on major characteristics (e.g., disease stage, current treatment status,) to reduce the unnecessary burden of contacting patients who will not screen in or of contacting patients who may be ill. Study staff will contact providers to obtain approval (as needed) to contact the potential participant. If the provider approves, a letter from the patient's provider will be sent to a candidate summarizing the research study. We will include a phone number for the patient to call to indicate that she is not interested in pursuing the study further.

A total of 15 patients will be recruited from Duke Cancer Center to complete study procedures.

Participants will have the opportunity to consent electronically via redcap database or by paper over the telephone. After completing a baseline assessment, participants will be sent sealed study materials along with the instructions regarding the study interventionist's name and contact information. All sessions will be conducted by trained interventionists with a Masters or doctoral degree in psychology or clinical social work and certified competent in the interventions by the PI. [name] will hold regular supervision sessions among the interventionists to ensure adequate quality of the delivered interventions. All supervision sessions are confidential; no identifiable information about participants is retained in supervision records.

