#### Risk/Benefit Assessment

Potential medical risks and discomforts: We do not anticipate any significant medical risks or discomforts to lung cancer patients who consent to participate in the study. Should the health status of a patient in a way that precludes further study participation, that participant will be able to withdraw from the study as needed (which will be stipulated in the consent form as per Duke University policy).

Potential psychological risks and discomforts: The study is not targeting treatment of psychiatric illnesses, and we do not anticipate that the participants will be at substantial risk of suicidality, self-harm, or harm to others. The PI is a licensed clinical psychologist and works in a research lab that has an in-place, IRB-approved procedure for the protection of research participants experiencing acute increases in distress which will be available throughout the duration of this project. All study staff will be trained in this existing procedure (which includes 24-hour phone access to the PI as needed).

A situation in which a study participant is at imminent risk of harming him/herself or others may necessitate involuntary reporting and intervention. This risk of loss of confidentiality will be discussed and disclosed to potential participants at the time of consenting. Because psychological interventions for emotional distress invariably require the patient to attend to discomfort and associated thoughts and

feeling, participation in the study will be associated with some risk of increased psychological distress, which may include discomfort with attention to unpleasant thoughts, feelings, or body sensations. Some individuals may experience an initial increase in undesirable feelings with increased attention to them. SST already contains procedures for identifying, anticipating, and minimizing discomforts that often characterize psychotherapy and related preventive interventions, and the interventionists will be thoroughly trained in how to use those techniques to simultaneously protect participants and assist them in gaining benefit from the intervention.

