#### Data Analysis & Statistical Considerations

Because this is a small pilot study with a small sample size power calculations are inappropriate. Below is a summary of the planned data analysis:

Descriptive statistics will be used to analyze SST-LC attendance, responses to questionnaire items, and sociodemographic data. Outcome measure data will be analyzed on an as per protocol basis. Standardized mean differences (with Hedges adjustment for small sample size) and 95% confidence intervals to examine the relative size of the intervention effect across the different measures. Scores are interpreted as positive intervention effects when the post-intervention values of negative affect are lower than baseline; and when post-intervention values of efficacy, affect, cognitive appraisal, coping, resilience, physical functioning and activity are higher than baseline. Psychological resilience and physical resilience self-report scores from baseline to 1-month follow-up will also be analyzed.

All quantitative analyses will be performed using IBM SPSS statistics software.

Participants enrolled in the study will complete participation across 2-4 months.

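### Does leaving the denominator of the 80% session target open let early stopping count as completion?

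*Combined protocol and SAP*

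**What the plan says.** The attendance hypothesis, under Purpose of the Study, reads "Participants will complete at least 80% of SST treatment sessions". It names no denominator and does not say whether the 80% applies to each participant or to average attendance.

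Design & Procedures describes "sessions that range between 8 (recommended minimum number of sessions) to a maximum of 12 sessions", so the length varies and the lower end is a recommendation. It lists four content areas spread over the course. The fourth begins "A maintenance plan is developed with each patient", but this is not called a completion criterion or tied to a session number.

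Subject Recruitment gives the size: "A total of 15 patients will be recruited from Duke Cancer Center to complete study procedures". Risk/Benefit Assessment provides for a change in health that prevents further participation, saying "that participant will be able to withdraw from the study as needed".

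Data Analysis & Statistical Considerations says "Descriptive statistics will be used to analyze SST-LC attendance". The same section says "Outcome measure data will be analyzed on an as per protocol basis", a sentence about outcome measures and not about attendance. It declines any power calculation because the study is a small pilot.

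**The concern.** A percentage target needs a denominator, and here the denominator can vary from person to person. If 80% is read against each participant's own course, and that course length is settled only after the person has stopped, then anyone attending 8 or more sessions scores 100%. A finished 8-session course and a 12-session course abandoned at 8 look the same in the data. The intended length could not be recovered reliably afterwards.

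At stake is how far the pilot's adherence result can be trusted. The 80% is the only numerical threshold in the hypotheses. Participants have stage III or IV lung cancer, so stopping partway is foreseeable, and the plan looks ahead to a larger randomised trial. An adherence figure that early stopping cannot lower would be a poor guide for that trial.

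**Working it through.** **Inputs.** Threshold 0.80 (Purpose of the Study); course length L from 8 to 12 (Design & Procedures); 15 participants (Subject Recruitment), taken here as 15 enrolled, although that sentence could also mean 15 completers. The 80% is a chosen threshold, so there is no derived figure to reproduce.

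**Step 1: sessions needed.** The smallest whole number k with k/L ≥ 0.80.

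| L | 0.8 × L | k | k/L |
|---|---|---|---|
| 8 | 6.4 | 7 | 87.5% |
| 9 | 7.2 | 8 | 88.9% |
| 10 | 8.0 | 8 | 80.0% |
| 11 | 8.8 | 9 | 81.8% |
| 12 | 9.6 | 10 | 83.3% |

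Six sessions fail even at the shortest length (6/8 = 75.0%). Ten pass even at the longest (10/12 = 83.3%). The choice of denominator affects only people who attend 7, 8 or 9.

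**Step 2: early stops whose classification changes.** Let a be sessions attended and L the intended length. Compare a/L with a/max(8, a), the score if the length is settled afterwards with 8 as its floor.

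| Attended | Intended length | Against intended length | Settled afterwards |
|---|---|---|---|
| 7 | 9, 10, 11, 12 | 77.8%, 70.0%, 63.6%, 58.3% | 7/8 = 87.5% |
| 8 | 11, 12 | 72.7%, 66.7% | 8/8 = 100% |
| 9 | 12 | 75.0% | 9/9 = 100% |

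That gives 4 + 2 + 1 = 7 combinations.

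**Step 3: what the settled-afterwards rule amounts to.** Under a/max(8, a), a participant passes exactly when a ≥ 7. A fixed denominator of 8 gives the same rule, since 7/8 passes and 6/8 fails. The lenient scoring therefore classifies people just as 80% of the recommended minimum would.

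**Step 4: bounds from attendance alone.** The number needed never falls as L rises (7, 8, 8, 9, 10). Whatever mix of lengths from 8 to 12 applies, the number of participants meeting the target lies between the number attending at least 10 and the number attending at least 7. Both counts come from the attendance distribution and need no planned length.

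**Step 5: size.** One participant is 1/15 = 6.7 percentage points. As an invented illustration, suppose 13 people attend every intended session of a 12-session course and two stop at 8 of 12:

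- denominator 8, or length settled afterwards: 15/15 = 100%;
- denominator 12, or intended length: 13/15 = 86.7%, exact (Clopper-Pearson) 95% interval 59.5% to 98.3%.

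The shift is 13.3 points, against an interval 98.3 − 59.5 = 38.8 points wide. If the 80% means average attendance, which the wording also permits, scoring against 12 gives (13 × 100% + 2 × 66.7%)/15 = 95.6%, well above 80%.

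**The case for a change.** The best case for a change is that it would be cheap and that the information is perishable. A few sentences and two recorded fields (intended number of sessions, and whether the maintenance plan was reached) would separate a finished short course from an abandoned long one. A count of sessions attended cannot do that. The silence on the denominator is a fact, the arithmetic above is correct, and early stopping is plausible in this population.

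What stands is that the denominator, and the choice between per-person and average attendance, are unstated, and that whoever reports the study must say which was used.

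The rest is weaker:

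- The harm needs two things the documents do not contain: an individual planned number of sessions, and a practice of resetting it after the person stops. With a fixed denominator of 8 or of 12 the timing question disappears.
- Three of the seven combinations involve 8 or 9 sessions, which already reach the recommended minimum. Counting those people as having met the target is defensible. Only the four cases with 7 attended remain, and 7 is 87.5% of that minimum.
- Treatment goals emerge during the exploration phase and are worked through in the phase that follows. A length written down at or before the first session could be a guess. Someone put down for 12 who properly finishes at 8 or 9 would score 66.7% or 75.0% and be marked as missing the target. That trades one misclassification for another, and recording the maintenance plan would show it without removing it.
- Using 8 as the default where no length was recorded would bring back the leniency complained of.

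**Conclusion.** The concern identifies missing detail, but no change to the plan follows. The result is open only for participants with 7, 8 or 9 sessions, at 6.7 points each. Attendance is descriptive, the plan sets no proportion of participants who must reach 80%, and no error rate, sample size or go/no-go decision depends on it. An analyst describing attendance will naturally show the distribution of sessions and say what the percentage is of. The counts at 7 or more and at 10 or more then give the result against 8 and against 12 and bound it for any length between. The proposed remedy of fixing an individual length at the start is a trade-off with no clear gain.

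This rests on three assumptions: course lengths stay within 8 to 12, although the lower end is only recommended; 15 is the number enrolled; and attendance is reported as a distribution and not merely as a single percentage. If a later trial used the 80% as a formal progression criterion, the definition would matter more.

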## Background & Significance

Resilience is defined as the capacity of people to effectively cope with, adjust, or recover from stress or adversity (physiologically, psychologically or socially). In the context of cancer across the disease continuum, resilience refers to an individual's protective attributes and/or personal characteristics. These attributes, which are thought to be modifiable, promote successful adaptation to cancer, including, meaning and purpose in life, sense of coherence, positive emotions, self-esteem, self-efficacy, cognitive flexibility, coping, and social support. Collectively these factors all positively correlate with quality of life, and may enhance physical functioning. Research evidence support findings that suggest prolonged stress and poor psychosocial functioning negatively impact physical health. For example, prolonged stress influences biological mechanisms that lead to hypertension and blood pressure reactivity, pro-inflammatory cytokines (e.g. C reactive protein), and the development of metabolic syndrome.

Healthcare providers and healthcare systems benefit from the knowledge and understanding of associations between psychological and physical functioning variables that promote resilience in older adult patients. These associations inform treatment, prevention, and intervention protocols through a biopsychosocial perspective. However, how resilience is studied, measured, and addressed among older adults living with serious, life-limiting illness such as advanced lung cancer is an understudied-- yet much needed area of research. In addition it is challenging to conceptualize how certain aspects of the resilience model apply to more chronic stressors.

Psychological Resilience, as noted above, is one component to enhance an older adult's quality of life. Physical resilience is yet another source to enhance quality of life. Using the NIA's definition of physical resilience as "a dynamic property which enables individuals to resist or recover from the effects of a physiological or stressor" (e.g., serious disease such as advanced lung cancer), I want to address in this proposal how I can examine the connection between psychological resilience and physical resilience in the context of a behavioral intervention to characterize different resilient phenotypes.

With the piloting of SST-LC underway with our study team, for this RCCN proposal I will 1) test measures of psychological and physical resilience on an sample of 15 older adults with late-stage lung cancer, and

2) test whether psychological resilience measures is associated with physical resilience measures in efforts to test prediction models in a future larger RCT study.

#### Design & Procedures

Fifteen older adults (ages 65 and older) will be recruited from clinics of the Duke Cancer Institute.

Older adults with lung cancer will receive the SST intervention with sessions that range between 8 (recommended minimum number of sessions) to a maximum of 12 sessions lasting on average of 30-45 minutes. The intervention will be delivered by video conference. The design is a single-arm study, with no control or placebo group condition.

The four content/topic areas that are covered across the 8-12 SST intervention sessions are as follows:

1) Orientation Phase of SST. Participants are provided with a rationale for treatment that focuses on the importance of self-regulation for well-being in the context of advanced cancer.

2) Exploration Phase of SST. This phase consists of having patients examine successful and unsuccessful interpersonal interactions, functional difficulties, and their self-evaluations and goal pursuit strategies while coping with advanced cancer. Patients then identify and analyze their explicit or implicit preferences for certain kinds of personal goals.

3) Adaptation Phase of SST. The patient and interventionist work together to address each treatment goal, using change strategies and compensatory strategies that include helping the patient to modify goals or to learn to pursue them via different means that are a better fit to their current life circumstances, physical, limitations, or personality traits.

4) A maintenance plan is developed with each patient. The maintenance plan includes a list of strategies to be used daily (e.g. self-monitoring forms), short-term goals (e.g. becoming more active in self-rewarding activities) and long-term goals.

#### Selection of Subjects

Patients will be recruited from clinics of the Duke Cancer Institute. Inclusion/Exclusion criteria are listed below. These will be determined by medical chart review to ensure that participant involvement is appropriate. We are utilizing the duke opt out policy for recruitment purposes.

#### Inclusion criteria:

Age  $\geq$  65 years

English-speaking

Patient has diagnosis of late stage (III-IV) lung cancer and is living at her/his home.

#### Exclusion criteria:

Unable to provide informed consent  
Visual or hearing impairments that preclude participation  
Serious mental illness

#### Subject Recruitment

Potentially eligible candidates will be identified from each oncology provider's clinic schedules via medical chart review. This pre-identification process involves pre-screening of patients using their medical records on major characteristics (e.g., disease stage, current treatment status,) to reduce the unnecessary burden of contacting patients who will not screen in or of contacting patients who may be ill. Study staff will contact providers to obtain approval (as needed) to contact the potential participant. If the provider approves, a letter from the patient's provider will be sent to a candidate summarizing the research study. We will include a phone number for the patient to call to indicate that she is not interested in pursuing the study further.

A total of 15 patients will be recruited from Duke Cancer Center to complete study procedures.

Participants will have the opportunity to consent electronically via redcap database or by paper over the telephone. After completing a baseline assessment, participants will be sent sealed study materials along with the instructions regarding the study interventionist's name and contact information. All sessions will be conducted by trained interventionists with a Masters or doctoral degree in psychology or clinical social work and certified competent in the interventions by the PI. [name] will hold regular supervision sessions among the interventionists to ensure adequate quality of the delivered interventions. All supervision sessions are confidential; no identifiable information about participants is retained in supervision records.

#### Risk/Benefit Assessment

Potential medical risks and discomforts: We do not anticipate any significant medical risks or discomforts to lung cancer patients who consent to participate in the study. Should the health status of a patient in a way that precludes further study participation, that participant will be able to withdraw from the study as needed (which will be stipulated in the consent form as per Duke University policy).

Potential psychological risks and discomforts: The study is not targeting treatment of psychiatric illnesses, and we do not anticipate that the participants will be at substantial risk of suicidality, self-harm, or harm to others. The PI is a licensed clinical psychologist and works in a research lab that has an in-place, IRB-approved procedure for the protection of research participants experiencing acute increases in distress which will be available throughout the duration of this project. All study staff will be trained in this existing procedure (which includes 24-hour phone access to the PI as needed).

A situation in which a study participant is at imminent risk of harming him/herself or others may necessitate involuntary reporting and intervention. This risk of loss of confidentiality will be discussed and disclosed to potential participants at the time of consenting. Because psychological interventions for emotional distress invariably require the patient to attend to discomfort and associated thoughts and

feeling, participation in the study will be associated with some risk of increased psychological distress, which may include discomfort with attention to unpleasant thoughts, feelings, or body sensations. Some individuals may experience an initial increase in undesirable feelings with increased attention to them. SST already contains procedures for identifying, anticipating, and minimizing discomforts that often characterize psychotherapy and related preventive interventions, and the interventionists will be thoroughly trained in how to use those techniques to simultaneously protect participants and assist them in gaining benefit from the intervention.

There are no known risks related to their administration, although these assessments may uncover strong and potentially difficult feelings about the subject's past or present emotional state. In previous studies (spearheaded by co-mentor [name]) involving over 1,000 patients, using similar self-report batteries, they have encountered little resultant distress. We will, however, train research staff to collect data to be sensitive to the nature of illness-related issues. When necessary, participants who experience psychological distress related to filling out self-report questionnaires will be referred for appropriate psychiatric or psychological care.

**Other risks:** The other risks of this study are those associated with confidentiality. In any research project of this type, there is some risk attendant to confidentiality of self-report data. To ensure confidentiality of data, all records will be identified by the participant's identification number, not by name. All raw data will be kept in a locked file cabinet. Protocols and completed measures will be coded by number only, for the purpose of data tabulation and analysis. Data will be stored in protected research computer servers/systems at Duke which employ strict procedures to ensure subject confidentiality. All data will be entered into the computer by study staff only, utilizing code numbers only for subject identification. All information given by the participants will be kept confidential. There will be only one exception to this strict confidentiality policy, which pertains to information obtained during the research assessment which would indicate that the participant is seriously suicidal and may pose a significant and acute risk of self-harm, or if there is a risk of elder abuse. Subjects will be informed of this exception, and will also be informed that such information will be shared with the P.I. of the study and their Attending Physician so that timely and appropriate arrangements for psychiatric assessment and care can be made. This information is included in the Informed Consent form.

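### The protocol does not separate stopping SST sessions from leaving the study or provide for assessment after sessions stop, so the before-after change may come mainly from patients who stayed well.

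*Combined protocol and SAP*

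**What the plan says.** The Risk/Benefit Assessment, under medical risks, covers a patient whose health changes so much that taking further part in the study is ruled out, and says "that participant will be able to withdraw from the study as needed". Withdrawal from the study is the only option it names.

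Design & Procedures describes the intervention as "sessions that range between 8 (recommended minimum number of sessions) to a maximum of 12 sessions lasting on average of 30-45 minutes", delivered by video. It adds: "The design is a single-arm study, with no control or placebo group condition".

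Data Analysis & Statistical Considerations states: "Outcome measure data will be analyzed on an as per protocol basis". It does not define that set, and it gives no rule for missing data, withdrawal or death. The effect measure is "Standardized mean differences (with Hedges adjustment for small sample size) and 95% confidence intervals". On later follow-up it says: "Psychological resilience and physical resilience self-report scores from baseline to 1-month follow-up will also be analyzed". Participation is expected to last 2 to 4 months.

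Purpose of the Study hypothesises that "psychological and physical resilience scores will improve from baseline to post-intervention as a function of receiving the SST intervention".

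No section says whether a patient who stops sessions early is still assessed, or when the post-intervention assessment falls for such a patient.

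**The concern.** Sessions and assessments are different burdens. A patient may no longer manage 8 to 12 video sessions of 30 to 45 minutes and still be able to answer questionnaires. The protocol does not deal with that patient. Staff would have to decide case by case, and the only option written down for declining health is leaving the study. Scores that are not collected cannot be recovered at analysis, whatever analysis set is chosen. Scores that are collected could still be left out of an undefined per-protocol set.

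This matters more here than in many pilots, for three reasons.

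- The background section defines physical resilience as resisting or recovering from a stressor and gives advanced lung cancer as an example. Decline from that disease is what would prompt withdrawal, so data are most likely to be lost in the patients whose resilience is being tested.
- Patients are 65 or older with stage III-IV disease, so decline within 2 to 4 months is plausible.
- There is no control group in which the same selection would show, yet the hypothesis credits improvement to SST.

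At stake are the baseline to post-intervention and 1-month changes. Also at stake is what the pilot can learn about whether the measures are feasible in patients who are declining.

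**Working it through.** **No figure to reproduce.** The plan states no power, effect size, SD or withdrawal rate, and it declines a power calculation. The sample size of 15 comes from Design & Procedures. Every other input below is an assumption.

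**Reading the sections together**

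1. Risk/Benefit Assessment: one named option for declining health, which is study withdrawal.
2. Design & Procedures: the number of sessions varies from 8 to 12, so a post-intervention time defined by the end of sessions has no fixed date for someone who stops early.
3. Data Analysis: per-protocol analysis, set undefined. The 80% attendance figure in Purpose of the Study is a hypothesis about adherence and is not linked to the analysis set.
4. Two separate steps can therefore remove a declining patient: the score is not collected, or it is collected and not analysed.

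**Illustration A: the sickest patients are lost.** Assume the true mean change is zero, the sickest fraction p is lost, and latent health correlates rho with change (bivariate normal). The apparent mean change in those retained, in SDs of change, is

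rho × phi(z_p) / (1 − p),

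where z_p is the p-quantile of the standard normal and phi is its density.

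| Lost | p | z_p | phi(z_p) | phi/(1 − p) | rho 0.3 | rho 0.5 | rho 0.7 |
|---|---|---|---|---|---|---|---|
| 2 of 15 | 0.133 | −1.111 | 0.215 | 0.248 | 0.07 | 0.12 | 0.17 |
| 3 of 15 | 0.200 | −0.842 | 0.280 | 0.350 | 0.11 | 0.18 | 0.25 |
| 5 of 15 | 0.333 | −0.431 | 0.364 | 0.545 | 0.16 | 0.27 | 0.38 |

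**Illustration B: no distributional model.** The mean change in those retained minus the mean change in all 15 equals (share lost) × (gap in mean change between those retained and those lost).

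- 2 lost: 0.133 × 0.5 = 0.07 SD; 0.133 × 1.0 = 0.13 SD.
- 3 lost: 0.20 × 0.5 = 0.10 SD; 0.20 × 1.0 = 0.20 SD.
- 5 lost: 0.333 × 0.5 = 0.17 SD; 0.333 × 1.0 = 0.33 SD.

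The two approaches agree in order of size. If all 15 were assessed and analysed, this excess would be zero.

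**Precision, for scale.** The 95% CI half-width for a mean change, in SDs of change, is t(0.975, n − 1)/√n. At n = 15 it is 2.145/√15 = 0.55; at n = 12 it is 2.201/√12 = 0.64.

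**How likely are such losses?** Under an assumed 10% loss per patient, the binomial chance of losing at least 3 of 15 is 18%; under 20% it is 60%.

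**The case against.** A reader might infer that the protocol requires patients too ill for sessions to stop being assessed. It does not say so. The sentence is a permission, it concerns health that prevents taking part in the study rather than in the sessions, and it stands in a section on risks and participant rights. A patient who can still answer questionnaires is arguably outside it. That objection stands: the defect is silence, not an instruction to stop collecting data. The consent form, to which the protocol refers for withdrawal, is not among the pages available and may say more.

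A reader might also infer that the association between psychological and physical resilience will exclude decliners. The documents do not support this. The association is not tied to follow-up, and it can be estimated at baseline in everyone assessed then.

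Third, more data collection alone might change nothing, because the undefined per-protocol set could drop the extra scores. That stands, and it is why the fix has two parts.

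Fourth, the withdrawal rates and correlations are assumed, the direction of bias is plausible rather than shown, and the illustrated bias for 2 or 3 losses is well inside the confidence interval half-width. The first two parts stand. The last is a weaker defence: a wide interval does not correct a shifted centre, and the plan reports the interval as describing the intervention effect.

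Finally, remote questionnaires do not recover physical performance measures, which the purpose section names as resilience indicators. That limit stands.

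**Conclusion.** The concern holds as a gap in the plan. Stopping sessions is not separated from leaving the study, continued assessment is not provided for, and the per-protocol set is undefined. Followed as written, the plan can yield before-after and 1-month changes that come mainly from patients who stayed well. They are biased toward improvement if those lost would have changed less favourably, and with a single arm nothing in the data would reveal it.

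The size cannot be derived from the documents. Illustratively it is about 0.07 to 0.25 SD of change for 2 to 3 of 15 lost, assuming that the true mean change is zero, that exactly the sickest are lost, and that health correlates 0.3 to 0.7 with change. Fewer losses, or losses unrelated to change, would make it smaller. The point should be addressed before recruitment because uncollected scores cannot be recovered.

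**What to change.** **Risk/Benefit Assessment.** State that a patient who stops SST sessions is invited to complete the remaining post-intervention and 1-month self-report measures remotely, unless they decline. For early stoppers, set the post-intervention assessment at a date fixed in advance from baseline, for example when their sessions were expected to end. Check that the consent form agrees.

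**Data Analysis & Statistical Considerations.** Define the per-protocol set. Beside it, report the change in all enrolled patients with post-baseline data. Give counts and reasons for loss (for example health, death, distress, refusal), and the baseline scores of patients with and without follow-up.

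Both parts are needed: the first makes the scores exist and the second makes them count.

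**Cost.** Protocol wording, consent wording if needed, and a few remote questionnaires. The downside is a small burden on ill patients, who may decline. Physical performance measures and data after death may still be missing, so some selection can remain, but it will be visible. When sessions stop, and the patient's right to withdraw, are unchanged.
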